After self-report questionnaires are completed, participants will then complete the baseline clinical interview (paper version of “LIMBIX - Measure - MINI Neuropsychiatric Interview.pdf”) conducted by a study team member who is not the ultimate research therapist. The clinical interview will generally take about 15 to 25 minutes. This interview will be videotaped to conduct reliability assessment on the diagnoses.

Participants who meet the study eligibility criteria will next be contacted by phone by another study team member within a week to receive their random assignment to either the virtual reality exposure therapy condition or the waitlist control condition and to schedule their treatment planning session. Participants in the immediate treatment group will be invited to start treatment soon after the baseline assessments, whereas those in the waitlist control condition will be invited to start this treatment 8 weeks later. The script “LIMBIX - Scripts - Study Therapist to Subject” will be used to facilitate this process.

Within a day the intake assessor completes the initial assessment for an eligible participant, the coordinator will (1) randomly assign the eligible participant who had just completed the interview to their treatment condition, (2) call the participant to inform them of their study condition, and (3) inform their research therapist assigned to be in charge with conducting the 8 to 10 50-minute weekly treatment planning and therapy sessions.

As participants assigned to the treatment condition will begin therapy immediately, the coordinator will communicate this message to the research therapist within a day of the initial assessment.

On the other hand, participants assigned to the waitlist control condition will begin therapy 8 weeks later, and the coordinator will communicate this message within a few weeks after the initial assessment visit.

Once the research therapist receives the message from the coordinator to start scheduling treatment with a particular participant, he or she is expected to contact the participant and set up an appointment within the next one or two weeks depending on their availability.

Step 3: Treatment Planning

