In each session, the participant will come in and be exposed to different social scenarios virtually. Each study team member follows a script for each session to direct them to the scenario (“LIMBIX - Scripts - Each Session - V1.docx”). The team member thus functions mainly as a facilitator who will ensure that the correct brief social scenario is presented to the participant for both the general social skills exposure therapy (“LIMBIX - Scripts - Phobia General Social Interactions.docx”) and job interview exposure therapy (“LIMBIX - Scripts - Phobia Job Interview.docx”). Note that there are seven social scenarios for both forms of exposure therapy. The social scenarios build on each other in terms of the level of difficulty. Therefore, we will continue with the next scenario only after the participant says he or she feels ready to expose themselves to the next scenario. After each scenario, the study team member records participants' subjective units of distress using the “LIMBIX - In-session SUDS Ratings”. Ten minutes before the 50-minute session ends, the team member assigns homework in between the

weekly sessions using a standard script (“LIMBIX – Between Session Homework”). Homework is meant to help participants generalize the skills they learn from this treatment to their everyday life situations.

Step 4: Assessing and Adjusting Treatment

We aim to ensure that each participant finds the intervention to be helpful and to identify the need to discontinue due to various reasons (e.g., participant finds the intervention is unhelpful, causes adverse side effects or severe cybersickness). Participants will thus complete the System Usability Scale on the first, fourth, and last week of the 8-10 session intervention. This will provide a measure of their experience and will help to facilitate a conversation with the therapist about their experience. Scores below a 70 (Bangor, Kortum, & Miller, 2009) would indicate that the usability of the tool was below average and will signify that further discussion is needed to identify if the use of the digital tool should be discontinued. Please note that efforts will be made to problem solve usability concerns with the participant when possible, as participants will have varying levels of technological comfort the therapist will work to personalize this process to the participants’ needs.

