During the session, some research personnel will assist with helping participants to respond if the participants have problems responding to the system (“LIMBIX - Scripts - RA Prompts If Participant Gets Stuck.docx”).

Step 5: Between-Session Symptom Assessment

To monitor treatment progress, participants will complete between-session symptom assessments at the end of each session (“LIMBIX - Measure - Between session symptom assessments.pdf”). Participants will also be asked to engage in practice of skills they learn in treatment between sessions (refer to “LIMBIX – Between-Session Homework”).

This applies to participants in the treatment, but not waitlist, condition. For participants placed on the waitlist, this applies only once treatment has started.

Step 6: Termination

The research therapist will work with participants to determine therapy goals at the start of treatment, and will work with them to monitor progress on these goals throughout treatment. Generally, treatment length will span 8 to 10 sessions, depending on the participant’s symptoms, response to treatment, and therapists’ clinical judgment.

Step 7: Final Assessments

Participants will be asked to complete the follow-up questionnaire packet (see “LIMBIX - Measure - Follow-up questionnaire packet.pdf”). This packet will be provided to them prior to their final session, and the final interview (conducted online “LIMBIX - Measure - Final interview.pdf”) will be included in the termination session. The final interview session will be administered at the end of Session 10.

Three and six months after treatment, participants will be contacted online to complete the 3-month and 6-month follow-up questionnaires (see “LIMBIX - Measure - 3-month post-treatment.pdf” and “LIMBIX - Measure - 6-month post-treatment.pdf” accordingly). At this time, participants will only complete self-report measures online.

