7.3 Duration of Participation

Describe the duration of an individual subject’s participation in the study.

We determined the length of time needed to complete the assessments. Based on this, it is predicted that the baseline assessments will be completed in 90 minutes, and the assessments at the end of treatment and 3- and 6-month post should take between 30 minutes to complete. In addition to time spent on assessments, participants will attend 8 to 10 sessions of weekly therapy sessions that will each be 50 minutes long. Note that the between-session measures are done at the end of each session. The frequency of treatment sessions will be determined by the participant's presenting concerns, but the following presents a reasonable estimate for most clients with social anxiety disorder who meet the study eligibility criteria.

Initial visit assessments:	60 minutes
3- month post-treatment assessments:	15 minutes
6- month post-treatment assessments:	15 minutes
8-10 treatment sessions:	$50 \times 10 = 500$ minutes
Final visit assessments:	10 minutes
Total time (approximate):	600 minutes

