8.3 Statistical methods

Describe the statistical methods (or non-statistical methods of analysis) that will be employed.

We will conduct a series of growth curve analyses to test for treatment efficacy. We will use the R packages 'lme4' (Bates, Maechler, & Bolker, 2012), 'lmerTest' (Kuznetsova & Brockhoff, 2014), and 'lavaan' (Rosseel, 2012) to calculate the growth trajectories for each participants. We will test for the impact of time using participants' scores at post-treatment, and at 6-month and 12-month follow-ups. We intend to perform separate models for each of the study outcome measures.

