Participants involved in this study will be asked to discuss difficult topics including current symptoms, past trauma, substance use, and psychiatric history. Despite the discomfort this may cause, this risk remains minimal as the procedures involved in the study are similar to those that individuals would encounter when engaging in any other mental health treatment.

Circumstances under which the study will be ended to prevent future risk:

The study will be ended if the protocol is shown to cause unnecessary harm to participants without any compensatory benefit. The Beck Anxiety Inventory (BAI; Beck & Steer, 1993) will be used to assess changes in symptoms every week. If no response, or negative response, (as operationalized as a 15% increase in severity on BAI scores for two consecutive sessions after initial adjustment to treatment has been made) continues for at least 5 participants, or if at least 5 participants are referred out due to requiring more care, the study will be stopped. This figure was chosen as controlled studies of single-diagnosis treatment trials often show that 5-10% of the study populations may exhibit an increase in symptoms while participating in a therapy study and 35- 40% report little benefit (Hansen, Lambert, & Forman, 2002). Given that the community population served by this study may be more complex than the populations seen in clinical trials the number was slightly increased.

It is expected that some participants will see a temporary increase in symptoms over the course of treatment due to the need to discuss difficult emotional information in treatment. To help ensure that any of the participant's concerns are addressed and that the treatment offered is responsive to the participant's needs, ongoing symptom monitoring will assist with the identification of individuals who do not appear to be benefiting from treatment and adverse effects will also be monitored through the assessment process (i.e., through the use of the Negative Effects Questionnaire; Rozental, Kottorp, Boettcher, Andersson, & Carlbring, 2016). This monitoring will also allow for a collaborative discussion with study participants so that adjustments can be made in their treatment as needed. If an individual participant becomes an imminent risk to themselves or others, their participation in the study will end and they will be referred to an appropriate level of care. We will ask such

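### The waitlist has no scheduled symptom assessment between baseline and its own VRET, so primary question 1 has no untreated comparator

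*Combined protocol and SAP*

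**What the plan says.** Hypothesis 1 (section 22.1), primary question 1 (section 22.2) and the design statement in 7.1 all set VRET against a waitlist control. Both arms complete baseline measures before assignment. Section 7.2, Step 2 then says "participants assigned to the waitlist control condition will begin therapy 8 weeks later".

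The later symptom measures are these:

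- **Between-session measures (7.2, Step 5)**, taken at the end of each session: "This applies to participants in the treatment, but not waitlist, condition. For participants placed on the waitlist, this applies only once treatment has started".
- **Final questionnaire packet (7.2, Step 7):** "This packet will be provided to them prior to their final session".
- **Follow-up questionnaires (7.2, Step 7):** three and six months after treatment.

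Section 7.3 budgets time for the initial, final, 3-month and 6-month assessments and for the sessions. Section 8.3 tests the effect of time using "scores at post-treatment, and at 6-month and 12-month follow-ups". It names neither an end-of-wait score nor baseline. Its 6- and 12-month follow-ups also disagree with the 3 and 6 months in 7.1 and 7.2, which is a separate inconsistency.

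**The concern.** A waitlist controls for change without treatment only if it is measured while still untreated, at a time when the other arm has been treated. Baseline cannot serve, because it precedes assignment. If the next scheduled waitlist measure comes after its own VRET has begun, a between-arm comparison estimates the effect of receiving VRET later.

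An effective therapy could then show no difference between arms, and that null could be read as failure. Primary question 2 has the same problem, since by follow-up the waitlist has also been treated. Hypothesis 2 avoids it only because it asks about maintenance among VRET recipients.

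**Working it through.** **1. Symptom assessments by arm, from 7.2**

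| Assessment | Immediate arm | Waitlist |
|---|---|---|
| Baseline | untreated | untreated |
| During the 8-week wait | end of each session | none |
| Between-session measures | from session 1 | from its own session 1 |
| Final packet | before own last session | before own last session |
| 3 and 6 months | after own treatment | after own treatment |

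Scheduled waitlist assessments after baseline and before VRET: 0.

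**2. Time budget in 7.3.** The listed items are 60 + 15 + 15 + 500 + 10 = 600 minutes, which reproduces the stated total. None of them is an end-of-wait assessment.

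**3. Common clock from baseline.** Inputs from 7.2: weekly sessions, 8 to 10 of them, an 8-week wait, and a first appointment taken as 0-2 weeks after the therapist is told to schedule. The last session falls 7-9 weeks after the first.

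- Immediate arm: (0 to 2) + (7 to 9) = weeks 7-11.
- Waitlist: (8 to 10) + (7 to 9) = weeks 15-19.

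The waitlist's first final packet therefore follows nearly a full course of VRET.

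**4. What a post-treatment contrast estimates.** Let *d* be the immediate effect in SD units and *k* the delayed effect as a share of it. Assuming no other change between the two calendar windows, the expected difference is (1 - k) × d. At k = 1 it is 0 for any d. With d = 0.229 (step 5), it is 0.1 × 0.229 = 0.023 SD at k = 0.9 and 0.2 × 0.229 = 0.046 SD at k = 0.8.

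**5. What an end-of-wait contrast could detect.** Section 8.2 gives 300 + 300 + 150 = 750 participants, 80% power and two-sided alpha 0.05, but no numerical effect size. Back-solving 300 v 300 gives d = (1.960 + 0.842) × sqrt(2/300) = 0.229. This is an assumption, as are the baseline-outcome correlation r = 0.5 and no dropout.

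The baseline-adjusted SE is sqrt((1 - r²)(1/n1 + 1/n2)):

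- both VRET arms v waitlist (600 v 150): sqrt(0.75 × 0.00833) = 0.0791
- one VRET arm v waitlist (300 v 150): sqrt(0.75 × 0.0100) = 0.0866

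By week 8, counting that week's session, the immediate arm has had 9, 8 or 7 sessions for starts at weeks 0, 1 or 2. That is 90%, 80% or 70% of a 10-session course. Power from the noncentral t distribution, with the effect accruing linearly over sessions:

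| Share of d = 0.229 accrued | 600 v 150 | 300 v 150 |
|---|---|---|
| 100% | 0.825 | 0.752 |
| 90% | 0.741 | 0.661 |
| 80% | 0.639 | 0.560 |
| 70% | 0.526 | 0.455 |

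At full effect with r from 0.3 to 0.7, power runs from 0.748 to 0.939 (600 v 150) and from 0.669 to 0.893 (300 v 150). At an assumed d = 0.5, r = 0.5 and 70% accrued, it is 0.993 and 0.981.

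**The case against.** Several readings favour the plan.

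- **Intent.** Section 7.1 clearly means to compare the arms over the treatment period. It schedules no measurement, so the intent has no data behind it.
- **Session 1 as a proxy.** Step 2 of 7.2 refers to a treatment planning session and to "8 to 10 50-minute weekly treatment planning and therapy sessions". If session 1 is planning only, the waitlist's first end-of-session score, at about weeks 8-10, could approximate an untreated value. But Step 3 says "In each session, the participant will come in and be exposed to different social scenarios virtually", and 8.3 does not use that score. The ambiguity is real, but it does not amount to a planned comparator.
- **Weekly anxiety inventory.** Section 11.0 says the Beck Anxiety Inventory "will be used to assess changes in symptoms every week" and names no arm. Its stopping rule, however, counts consecutive sessions after adjustment to treatment, and a waiting participant has none. If it is meant to cover the wait, 11.0 and Step 5 must be reconciled.
- **Wording of Step 5.** The exclusion directly follows a sentence on homework, so its reach could be argued. Even if it covered homework alone, the measures are taken at the end of sessions, which the waitlist does not yet attend.
- **Section 8.3 specifies no between-arm contrast.** True. The finding concerns any such contrast at the time points it names.
- **The zero difference is conditional.** Also true. The waitlist's final packet comes about 8 weeks later, so natural change, or the outside care that 7.1 permits, could produce a difference even at k = 1. That difference would not be the effect of VRET against no treatment.
- **The power figures are partial.** They assume no dropout. A 20% loss (also assumed) lowers full-effect power to about 0.74 (480 v 120) or 0.66 (240 v 120). The 70-90% accrual applies to 10-session courses. For 8 sessions it is 87.5-100%, giving about 0.72-0.83 or 0.64-0.75. These figures bear on the remedy; the gap does not depend on them.

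The questionnaire attachments are not in the documents. If one is an end-of-wait form, 7.2 and 8.3 still neither schedule nor analyse it.

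**Conclusion.** The concern holds and must be fixed. Followed exactly, the plan yields no post-baseline score from an untreated waitlist participant, so primary question 1 cannot be answered as posed and primary question 2 has no untreated comparison. This rests on the schedule in 7.2, 7.3 and 8.3 and needs no numerical assumption.

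The zero expected difference at post-treatment does need two assumptions: an equal effect in both arms, and no other change between about weeks 7-11 and 15-19.

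The missing element is an assessment. Whether the planned numbers suffice for the new contrast depends on an effect size that 8.2 does not state. Under the illustrative 0.229 SD and r = 0.5, power is about 0.46-0.83 across the comparisons and accrual shares tabulated. At 0.5 SD it is at least 0.98. No analysis can recover the untreated scores once waitlist participants have begun therapy.

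**What to change.** 1. In 7.2, 7.3 and 8.3, add one administration of the existing online self-report packet to both arms, at a common time since assignment, at the end of the wait and before any waitlist participant's first session.
2. In 8.3, make the baseline-adjusted between-arm difference at that time the analysis of primary question 1. Name the symptom scale, since the plan designates no primary measure, and confirm that it is also collected at baseline.
3. State whether session 1 is planning or exposure, and whether the weekly inventory in 11.0 runs during the wait.
4. The sponsor should reconcile the 8-week wait with the 8-10 session course, because some immediate-arm participants will still be in treatment at the new time point.
5. Align primary question 2 with hypothesis 2, or state its comparator once the waitlist has been treated.

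**Cost.** Section 7.3 gives 10 or 15 minutes per later assessment in its list, while its text says "the assessments at the end of treatment and 3- and 6-month post should take between 30 minutes to complete". At 10-30 minutes, the addition is 750 × 10/60 = 125 to 750 × 30/60 = 375 participant-hours. Repeating the whole baseline self-report battery, about 40 minutes in 7.2, would take 750 × 40/60 = 500 hours, but only the measures to be analysed need repeating. The participant time stated in 14.0 and the consent information would need a matching update.

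**Downside.** Under linear accrual over 10 sessions, 10-30% of the effect would not yet be visible at week 8. The contrast would be diluted, but it would still be against untreated participants.

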7.3 Duration of Participation

Describe the duration of an individual subject’s participation in the study.

We determined the length of time needed to complete the assessments. Based on this, it is predicted that the baseline assessments will be completed in 90 minutes, and the assessments at the end of treatment and 3- and 6-month post should take between 30 minutes to complete. In addition to time spent on assessments, participants will attend 8 to 10 sessions of weekly therapy sessions that will each be 50 minutes long. Note that the between-session measures are done at the end of each session. The frequency of treatment sessions will be determined by the participant's presenting concerns, but the following presents a reasonable estimate for most clients with social anxiety disorder who meet the study eligibility criteria.

Initial visit assessments:	60 minutes
3- month post-treatment assessments:	15 minutes
6- month post-treatment assessments:	15 minutes
8-10 treatment sessions:	$50 \times 10 = 500$ minutes
Final visit assessments:	10 minutes
Total time (approximate):	600 minutes

8.0 Participant Numbers and Statistical Plan

8.1 Number of Participants

Indicate the total number of participants to be accrued.

If applicable, distinguish between the number of participants who are expected to be enrolled and screened, and the number of participants needed to complete the research procedures (i.e., numbers of participants excluding screen failures.)

750 participants

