3.3.2 Follow-up for withdrawn participants

Describe when and how to withdraw participants from the study; the type and timing of the data to be collected for withdrawal of participants; whether and how participants are to be replaced; the follow-up for participants withdrawn from investigational treatment.

Participants are free to withdraw from the study at any point in time. Data will be collected up to the point the participant expresses his/her wish to withdraw. If a subject withdraws from the study, we will not ask participants to continue with study procedures (post and follow-up assessments). Further, as per FDA regulations, we will not remove study data collected up to the point of withdrawal.

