7.2 Study Procedures

Provide a description of all research procedures being performed and when they are being performed (broken out by visit, if applicable), including procedures being performed to monitor participants for safety or minimize risks. Include any long-term follow-up procedures and data collection, if applicable.

Describe where or how you will be obtaining information about participants (e.g., medical records, school records, surveys, interview questions, focus group topics, audio or video recordings, data collection forms, and collection of specimens through invasive or non-invasive procedures to include the amount to be collected and how often). Add any data collection instruments that will be seen by participants to your study in CATS IRB (<http://irb.psu.edu>) in the “Supporting Documents” page.

Step 1: Phone Screening

Potential participants will first complete a brief phone screen to ensure they meet the basic criteria for the study. During the phone screen, the participant will be asked to provide a brief description of their presenting problem, as well as some basic information about their age to ensure they meet some of the inclusion criteria for the study (over the age of 18 and seeking help for social anxiety treatment).

Researchers will administer the script before scheduling the initial assessment (see “LIMBIX – Screening Consent - Phone.docx” under recruitment materials).

Step 2: Initial Assessment

Those that appear to meet some of the criteria based on the phone screen will be scheduled for an in-person initial assessment. The waiting period between the initial phone screen and appointment for the baseline assessment will depend on the availability of the participant and study team member conducting the baseline assessment.

During the initial assessment visit, participants will review the study consent with a study team member (“LIMBIX - Baseline Assessment Script” done online). Once consent is obtained, participants will be instructed to complete the baseline self-report questionnaires using a tablet or computer in one of the clinic or laboratory rooms at the Moore building, which will link to the Qualtrics questionnaires. The self-report assessments will take approximately 40 minutes.

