8.2 Sample size determination

If applicable, provide a justification of the sample size outlined in section 8.1 – to include reflections on, or calculations of, the power of the study.

The proposed study is focused on examining the efficacy, acceptability, feasibility, and the experience of the patient when using virtual reality in treating job interview phobia. The number of participants (300 per intervention condition; 300 General Social Skills Training; 300 Job Interview Phobia; 150 Waitlist Control) was based on Kampmann et al. (2016) who conducted a virtual reality study with adults with social phobia and used similar primary outcome measures. In their study, their power calculations estimated that 300 participants/per intervention group would be sufficient to find significant differences (two sided-power, power= 80%, alpha -0.05, G*Power 3.2) based on an effect size of exposure therapy found in a meta-analysis (Powers et al., 2008).

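### The total of 750 is the bare sum of the three groups, so the stated 80% power carries no stated allowance for participants who withdraw before giving post-treatment scores

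*Combined protocol and SAP*

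**What the plan says.** Section 8.1 answers the question on sample size with one figure, "750 participants". The form's instruction there asks the author, if applicable, to "distinguish between the number of participants who are expected to be enrolled and screened, and the number of participants needed to complete the research procedures". The answer makes no such split.

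Section 8.2 lists the groups as "300 per intervention condition; 300 General Social Skills Training; 300 Job Interview Phobia; 150 Waitlist Control". It justifies them from an earlier virtual reality trial in social phobia, reporting that "their power calculations estimated that 300 participants/per intervention group would be sufficient to find significant differences", with the settings "two sided-power, power= 80%, alpha -0.05, G*Power 3.2". It points to a meta-analysis for the effect size but does not give the value. It states no rate of screen failure or dropout.

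Other sections describe how participants are lost:

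- Section 7.2, Step 2: "Once consent is obtained, participants will be instructed to complete the baseline self-report questionnaires". The diagnostic interview that settles eligibility follows, and only those found eligible are randomised.
- Section 3.3.1 removes participants for repeated non-attendance or when they need more intensive care than the study can give.
- Section 3.3.2 says of those who withdraw that "we will not ask participants to continue with study procedures (post and follow-up assessments". Data already collected are kept. Replacement is not described, although the form asks about it.
- Section 8.3 fits growth models to post-treatment and follow-up scores.

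**The concern.** One number serves both as the total to be accrued and as the group sizes that support the power claim. The two agree only if nobody is lost between the point of counting and the post-treatment assessment. The protocol itself expects losses, and section 3.3.2 ends outcome collection at withdrawal.

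At stake is how far the 80% can be trusted. A reader of section 8.2 would take it as the power of the data the trial expects to have. As written, it is a figure for complete groups of 300, quoted without an effect size, and it is not stated for the comparison with waitlist in the first hypothesis.

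**Working it through.** **Inputs from the protocol.** Groups 300/300/150, power 80%, two-sided alpha 0.05 (section 8.2); total 750 (section 8.1). The effect size, dropout rate and screen-failure rate are not given.

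**The total.** 300 + 300 + 150 = 750, so the sum is right and contains no margin.

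**The 80%.** It cannot be reproduced without an effect size, so I inverted the usual two-sample formula (normal approximation, standard deviation 1):

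d = (1.960 + 0.842) × √(1/300 + 1/300) = 2.802 × 0.08165 = 0.229.

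This is the effect at which 300 v 300 has exactly 80% power. It is an assumption, not a figure from the protocol.

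**Power after loss.** Power = Φ(d / √(1/n₁ + 1/n₂) − 1.960), with each group multiplied by (1 − loss). I assume equal loss in all groups and that a lost participant adds nothing to the comparison. The first hypothesis sets VRET against waitlist. Reading this as the two VRET groups pooled gives 600 v 150.

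| Loss (assumed) | Left in groups | 300 v 300 | Pooled 600 v 150 |
|---|---|---|---|
| 0% | 300/300/150 | 80.0% | 70.7% |
| 10% | 270/270/135 | 75.7% | 66.2% |
| 20% | 240/240/120 | 70.7% | 61.1% |
| 30% | 210/210/105 | 65.0% | 55.4% |

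For example, at 20% loss the pooled comparison is 480 v 120: √(1/480 + 1/120) = 0.1021; 0.2287/0.1021 = 2.241; Φ(2.241 − 1.960) = 61.1%.

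The last column starts at 70.7%, not 80%, because the waitlist group is smaller. That gap of about 9 points is not due to loss. Loss accounts for the further 4.5, 9.6 and 15.3 points.

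**Other effect sizes.** The effect needed for 80% in the pooled comparison is 2.802 × √(1/n₁ + 1/n₂): 0.256 with no loss, then 0.270, 0.286 and 0.306 at 10, 20 and 30% loss. For a single VRET group against waitlist at 20% loss (240 v 120), power is 76.5% at d = 0.3, 94.7% at d = 0.4 and 99.4% at d = 0.5.

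**Stage of counting.** If 750 is counted at randomisation, only later loss matters. If it is counted at consent, failures at the interview also come off. As an illustration with assumed rates of 20% screen failure and 20% loss, 750 × 0.8 × 0.8 = 480 remain (192/192/96). At d = 0.229 that gives 61.1% for 192 v 192 and 51.8% for 384 v 96. The protocol does not say which stage applies.

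**The case against.** The strongest reply is that the shortfall in power is built into the assumption. Fixing d so that 300 v 300 gives exactly 80% means any loss must take it below 80%. Section 8.2 claims only that 300 is sufficient, and with a larger effect the design keeps more than 80% after substantial loss. This stands: the percentages are conditional. But the sponsor cannot rely on a larger effect while section 8.2 states none.

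Four further points limit what can be claimed.

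- A reader might infer that consent before the interview must shrink the groups. Groups exist only after eligibility is confirmed, so 750 may well count randomised participants, and then screen failures cost nothing. The subject-pool candidates are also pre-screened by questionnaire (section 4.1), and all candidates by phone (section 7.2, Step 1).
- A reader might infer that withdrawn participants supply no outcome data at all. Data up to withdrawal are kept, and session symptom measures exist once treatment starts. However, waitlist participants do not complete those measures while waiting, and section 8.3 does not name them.
- Section 8.2 speaks of numbers of participants, not of analysed or completing participants. The earlier trial's 300 might already include attrition; the protocol does not say. What can be said is that no allowance is stated.
- The 300 v 300 comparison sets the two VRET groups against each other, which no hypothesis does. The VRET v waitlist column is therefore the relevant one.

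**Conclusion.** The point holds in a limited form. Sections 8.1 and 8.2 use the same 750 as accrual total and as the sizes behind the power statement, while sections 3.3.1, 3.3.2 and 8.3 together mean that any withdrawal before post-treatment leaves fewer than 300/300/150 with the modelled scores.

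Under the effect implied by the protocol's own settings (d = 0.229), with equal loss and no information from those lost, 10 to 30% loss takes the VRET v waitlist comparison from 70.7% to between 66.2% and 55.4%. The loss rates are assumed.

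The documents do not support the stronger conclusion that the group sizes and 80% power are unattainable. That would need the total to be counted at consent, or a known effect size small enough for the losses to matter, and the protocol settles neither. The supportable statement is that 80% is not shown to survive any loss.

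**What to change.** In section 8.1, say whether 750 is the number consented or the number randomised, and add the number expected to provide post-treatment data.

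In section 8.2, state the effect size and its source, and the assumed loss. Replace the unqualified 80% with the power for VRET v waitlist at the number expected to provide post-treatment data, shown over a range of loss such as 10 to 30%. Any figure from the table above should carry its assumption of d = 0.229 until the sponsor supplies the intended effect.

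The cost is wording in two sections and, unless the intended effect is larger than the one implied here, a less favourable power figure. No increase in enrolment is needed for this correction. For scale only, keeping 300/300/150 with post-treatment scores would take 834, 938 or 1072 randomised at 10, 20 or 30% loss (750 divided by 0.9, 0.8 or 0.7, rounded up).
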